14.1. General Principal of Statistical Analysis

Information collected from subjects of the present clinical trial are analyzed in two forms: ITT (Intention-To-Treatment) and PP (Per-Protocol)

792793

794

795

796

1) ITT analysis group

The ITT population is defined as all randomized patients at 1 month after AMI, regardless of their adherence with the entry criteria, regardless of treatment they actually received, and regardless of subsequent withdrawal from treatment or deviation from the protocol¹⁹. Only some specific reasons that might cause an exclusion of a patient from the ITT population:

797 798

799

- No treatment was applied at all
- No data are available after randomization

800 801 802

803

804

•

2) PP analysis group

The PP population is the subset of ITT population consisting of all patients who receive and retain the treatment during 12 months after PCI¹⁹. Some specific reasons that might cause an exclusion of a patient from the PP population:

805806807

808

809

810

811

812

813 814

815 816

- Violation of entry criteria including inclusion and exclusion criteria
- Withdrawal of consent
 - Concomitant treatment of oral anticoagulant agent (vitamin-K antagonists or novel oral anticoagulants such as dabigatran, rivaroxaban, apixaban, or edoxaban) during the study period
 - Poor compliance
 - Conversion from ticagrelor + aspirin to clopidogrel + aspirin during RCT procedure and vice versa
 - Discontinuation of test or control drugs for 7 days or longer
 - * In the cases of withdrawal of consent, concomitant treatment of oral anticoagulation agent and poor compliance, their data will be used for statistical analyses until such events occur.

818		
819		
820	3) N	∕lissing data handling
821		Missing variables will not be imputed for planned analyses, except where otherwise
822		specified.
823		• The primary endpoint will be based on Kaplan-Meier estimates, which automatically
824		account for censored data.
825		• For sensitivity, purposes, missing data was imputed the most recent data (Last
826		Observation Carried Forward method).
827	4405	
828		Evaluation Standard
829		Efficacy Test Variable
830	•	Primary Endpoint
831 832	(Composite endpoint of MACCE (CV death, MI, or stroke) + BARC bleeding (type 2, 3 or 5) between 1 and 12 months after AMI
833	2)	Main Secondary Endpoints
834	1	BARC bleeding (type 2, 3, or 5) between 1 and 12 months after AMI
835	2	
836		between 1 and 12 months after AMI
837	3	Composite endpoint of MACCE (CV death, MI, or stroke) between 1 and 12 months after
838		AMI
839	3)	Other Secondary Endpoints
840	1	All-cause death between 1 and 12 months after AMI
841	2	CV death between 1 and 12 months after AMI
842	3	Recurrent MI between 1 and 12 months after AMI
843	4	Stroke between 1 and 12 months after AMI
844	(5)	Ischemia Driven Revascularization including PCI or CABG between 1 and 12 months after
845		AMI
846	6	Stent thrombosis (definite or probable) between 1 and 12 months after AMI
847		
848	14.2.2.	Exploratory Test Variable
849	Lab tes	st, cardiac echo, ECG, genetic test
850		

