9.3. Randomization

9.3.1. Subject Assignment and Randomization

Randomization will be performed to ensure the scientific validity of the clinical test. This will maximize the comparability of the test and control group and eliminate the subjectivity of the researchers in subject group assignment. Before PCI, a 250-325mg loading dose of aspirin is given to patients who are naïve to treatment and all patients receive a loading dose of ticagrelor 180mg. Discharge medication consists of aspirin 100mg once and ticagrelor 90mg twice per day. All patients receive treatment with aspirin plus ticagrelor for 1 month after the index PCI (screening period). At 30 ± 7days after index PCI, eligible patients were randomly assigned either to the 1) aspirin 100 mg plus clopidogrel 75mg daily (treatment group) or 2) aspirin 100 mg plus ticagrelor 90mg twice daily (control group) in a 1:1 ratio. Randomization will occur centrally. To randomize a patient, the investigative site will enter the subject into the designated electronic system and obtain the treatment assignment (clopidogrel + aspirin or ticagrelor + aspirin) in a 1:1 ratio. At 1 month visit after AMI, eligible subjects were assigned to each treatment group following an access to the interactive web-based response system (IWRS, Medical Excellence Inc., Seoul, Korea) by the investigator or designee. Randomization sequence was created by an independent statistician using SAS 9.3 (SAS Institute Inc. Cary, NC, USA) statistical software and was stratified by study center and type of AMI (STEMI or NSTEMI) and with a 1:1 allocation using hidden random block size.

404 405 406

407

408

409

410

411

412

413

389

390 391

392

393

394

395

396

397

398

399

400

401

402

403

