18.1 Subject Safety and Protective Measures

- Switching from Brilinta to Pregrel has no fixed guideline, but is a possible treatment based on the investigator.
- 1070 According to the guideline of the American Heart Association, acute myocardial infarction patie
- nts must take one of the three P2Y12 inhibitors (Clopidogrel 75 mg daily, Prasugrel 10 mg da
- 1072 ily, Ticagrelor 90 mg twice daily) after drug emission stent implantation for 1 year, but there is
- no guideline as to which drug to take as a priority. (11).
- According to the research switching to clopidogrel from prasugrel among acute coronary syndrome
- patients, the effect of platelet inhibition is significantly higher in Brilinta vs. Pregrel⁽¹⁰⁾.
- 1076 However, Pregrel has been used worldwide prior to the introduction of Brilinta and is currently
- 1077 being used. Pregrel has no limitations of use as it has lower antiplatelet inhibition rate vs.
- 1078 Brilinta, but has sufficient level of platelet inhibition to show effects of treatment.
- On the contrary, as the risk of bleeding can be higher for Brilinta with its strong antiplatelet i
- 1080 nhibition, this research aims to evaluate the efficacy and safety of the two drugs.
- Test drugs are already in-market and the investigator should be fully familiar with the indicated side-
- effects and precautions in the protocol. In case there are any serious adverse events during the test,
- the investigator should terminate the clinical trial for the subject, take appropriate measures and
- 1084 immediately inform the IRB.

10851086

1087

1088

1089

1090

10911092

1093

1094

10951096

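### Section 14.1 contradicts itself on who belongs to ITT, and its per-protocol set discards primary events that come before a stop or switch because the footnote keeping data up to the deviation omits those two reasons

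*Protocol*

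**What the plan says.** Protocol section 14.1 defines two analysis sets. The synopsis and section 8.2 (Analysis population) of the statistical plan use the same wording.

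- **ITT.** All randomised patients, "regardless of treatment they actually received". Two reasons may nevertheless lead to exclusion: "No treatment was applied at all" and "No data are available after randomization". Section 14.3.1 makes ITT the primary population.
- **Per protocol.** The subset of ITT made up of "all patients who receive and retain the treatment during 12 months after PCI". Listed exclusion reasons include entry violations, consent withdrawal, oral anticoagulant use, poor compliance, conversion between the two regimens, and "Discontinuation of test or control drugs for 7 days or longer". Section 14.3.1 has PP follow ITT, for the primary endpoint only.
- **Footnote to the PP list.** For consent withdrawal, anticoagulant use and poor compliance, "their data will be used for statistical analyses until such events occur". Conversion and stopping for a week or more are not named. The three reasons it does name also stand in the list as grounds for exclusion.

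Two other places bear on this. Section 9.3.1 states: "All patients receive treatment with aspirin plus ticagrelor for 1 month after the index PCI". Section 18.1 says that after a serious adverse event "the investigator should terminate the clinical trial for the subject", and section 15.1.3 counts death and hospitalisation as serious.

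**The concern.** The ITT definition gives two incompatible instructions about a patient who takes nothing after randomisation. Treatment is open label, so the choice would be made with the arm known. Everyone enters on ticagrelor and only the clopidogrel arm has to start a new drug, so the exclusion could fall more on that arm. It sits in the primary population.

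The PP problem is more concrete. A primary event is often the reason for a stop or switch. If the patient leaves the set because of the stop, the event leaves too, and the set is selected on the outcome it is meant to compare. Readers of a non-inferiority trial look to PP to support ITT. Agreement or disagreement between the two could then reflect the exclusion rule and not the drugs.

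**Working it through.** **1. The plan's own figures (section 7.3.2).** Bleeding after 30 days: ticagrelor 8.7 × 2.17 / (2.47 + 2.17) = 4.07%; clopidogrel 7.0 × 1.65 / (2.21 + 1.65) = 2.99%. Adding ischaemic rates of 5.28% and 6.60% gives 9.35% and 9.59%, a difference of +0.24 points. With 1,295 per arm that is about 121 and 124 patients with an event. These figures reproduce.

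**2. One patient traced through the rules.** A patient has a BARC 2 bleed in month 4 and stops the drug for 10 days. The stop is a listed PP exclusion, no exception is made for a stop caused by an endpoint, and the footnote does not name stopping. The patient and the bleed are both removed. The same holds if the patient converts to the other regimen.

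**3. Size if bleeders are dropped.** The documents give no stop or switch rate after a bleed, so the fraction f is assumed equal in both arms. As in the plan, ischaemic and bleeding rates are added without overlap. The PP rate is (total − f × bleeding) / (1 − f × bleeding):

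| f | Ticagrelor | Clopidogrel | Difference | Patients removed (ticagrelor / clopidogrel) |
|---|---|---|---|---|
| 0 | 9.35% | 9.59% | +0.24 | 0 / 0 |
| 0.25 | 8.42% | 8.91% | +0.49 | 13 / 10 |
| 0.50 | 7.47% | 8.22% | +0.75 | 26 / 19 |
| 0.75 | 6.50% | 7.52% | +1.02 | 40 / 29 |

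For f = 0.25: ticagrelor (9.35 − 1.0175) / (1 − 0.010175) = 8.42; clopidogrel (9.59 − 0.7475) / (1 − 0.007475) = 8.91.

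**4. The opposite movement.** If instead a fraction g of patients with an ischaemic event (including CV death) is dropped, the same formula with 5.28% and 6.60% gives +0.12 at g = 0.10, −0.06 at g = 0.25 and −0.39 at g = 0.50. Dropping 25% of both kinds gives 7.18% against 7.37%, or +0.19. Dropping 50% of both gives 4.90% against 5.04%, or +0.13 before rounding of the rates. To first order the joint shift is f × (4.07 − 2.99) − g × (6.60 − 5.28) = 1.08f − 1.32g. With f from 0.25 to 0.75 and g from 0.2 to 0.5 it runs from 0.27 − 0.66 = −0.39 to 0.81 − 0.264 = +0.55 points, so the sign is not fixed.

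**5. Effect at the margin.** Suppose clopidogrel is truly 3 points worse through ischaemic events (12.35% against 9.35%), with 1,295 per arm. The chance that PP passes at one-sided 0.05 is Φ((0.03 − d) / SE − 1.645), where d is the PP difference. Dropping 10% of patients with an ischaemic event gives d = 2.65 points and raises the chance from 5% to 8.8%. Also dropping 25% of bleeders gives d = 2.92 and 5.7%. Dropping 25% of bleeders alone gives d = 3.27 and 3.0%.

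**6. ITT.** Excluding a fraction u of an arm with event rate e changes that arm's rate p to (p − u × e) / (1 − u), which is lower than p only if e exceeds p. For illustration, let p = 12.35% and let 2% of the clopidogrel arm alone be excluded. With e = 9.35% the difference becomes 3.06 points; with e = 30% it becomes 2.64. The documents give neither u nor e, nor the split between arms. The second exclusion, no data after randomisation, makes no numerical difference: a patient censored at time zero adds nothing to a Kaplan-Meier estimate.

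**The case against.** A reader might infer three stronger points, which the documents do not support.

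- **That clopidogrel patients who never switch drop out of the primary set.** Someone assigned clopidogrel who stays on ticagrelor has been treated. That patient is more naturally a crossover, whom the definition keeps. The exclusion then reaches only a patient who takes nothing after randomisation, which can happen in either arm.
- **That PP removes everyone who dies.** Death is not a listed reason. A patient on assigned drug until death can reasonably be said to have retained it. The loss follows only if the 12-month wording is read literally.
- **That PP is biased towards non-inferiority, by a known amount.** Losing bleeds works against clopidogrel, which is the conservative direction here. Losing ischaemic events works for it. The two offset, so their separate extremes should not be joined into one range.

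There is more on the same side. PP is supportive and does not decide the trial. Any per-protocol set conditions on adherence. The exclusion reasons are worded permissively. Some stops might be classed as poor compliance and so come under the footnote. A 75% drop among bleeders is extreme: section 11.2 prefers managing bleeding without stopping ticagrelor where possible, and BARC 2 includes bleeds that only prompt evaluation.

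These points limit the size and the certainty. They do not remove the defect. Permissive wording leaves the exclusion to judgement in an open-label trial. Stopping is listed separately from poor compliance, so the overlap cannot be relied on. Section 18.1 gives a direct route from a serious event to the end of participation.

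**Conclusion.** The point holds in limited form. Section 14.1 contradicts itself on ITT, and the contradiction reaches the primary analysis. It could fall more on the arm that starts a new drug, but its size and direction cannot be worked out from the documents. The PP rules, as written, remove a primary event together with a patient who then stops for a week or more or converts. Whether deaths are also lost depends on how the 12-month condition is read.

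Under an assumed 25-75% loss of bleeders, equal in both arms, the planned PP difference of +0.24 moves to about +0.5 to +1.0 points, against clopidogrel. Loss of ischaemic events or deaths moves it the other way, so the net bias is uncertain in sign. It affects a supportive analysis, not the deciding one. The change should be made because the flaw lies in a stated rule and is cheap to repair.

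**What to change.** Amend section 14.1, the synopsis and section 8.2 of the statistical plan together.

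1. **ITT:** delete the never-treated exclusion, so that ITT is all randomised patients as assigned. Censor patients with no data at randomisation; the estimate does not change.
2. **PP:** exclude outright only patients who were ineligible at randomisation.
3. **Footnote:** extend it to conversion and to stops of a week or more. Count events up to and including the one that prompts the deviation, then censor. Remove the reasons it covers from the list of outright exclusions, so that no reason appears in both places.
4. **Retention:** state that death or an endpoint event is never a failure to retain treatment.

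The cost is definitions and minor reprogramming. No new data are needed and the sample size is unchanged. Censoring at a deviation may itself be informative, so PP should stay supportive.

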14.2.3. Safety Test Variable

Adverse event, vital sign, physical examination

853

851

852

854

855

856

857

858

859

860

861

862

863

864

871

875

876

877

878

879

880

881

882

883

14.3. Evaluation Method

14.3.1 Primary Endpoint Analysis

- The non-inferiority test between 1 and 12 months after AMI will be based on the Kaplan-Meier estimates. A 95% two-sided confidence interval will be computed for the difference event rate (clopidogrel + aspirin) – event rate (ticagrelor + aspirin). The clopidogrel group will be judged as non-inferior to the ticagrelor if the upper confidence limit is less than the predetermined noninferiority margin of 3% (absolute risk difference).
- The hypothesis of non-inferiority test will be based on the difference of proportions. Let r_T denote the true event proportion in the test arm (clopidogrel + aspirin) between 1 and 12 months, and $r_{\rm C}$ denote the true event proportion in the control arm (ticagrelor + aspirin) between 1 and 12 months. The hypotheses are

865
$$H_0$$
: r_T - r_C ≥ Δ

866
$$H_A: r_T - r_C < \Delta$$

- 867 The∆is the non-inferiority margin, and is taken to be 0.03. The test will be performed as a one-868 sided test at alpha=0.05.
- 869 The null hypothesis shall be rejected at alpha=0.05 if the one-sided p-value is less than 0.05. 870 When this occurs, the upper limit of the two-sided 95% confidence interval will be less than 3%.
- If the non-inferiority analysis passed the acceptance criterion, a superiority analysis will be 872 performed. Statistical superiority is achieved when the upper limit of the two-sided 95% 873 confidence interval of the risk difference is less than 0%. The type I error for this analysis is 874 protected by the non-inferiority analysis, and no alpha adjustment would be appropriate
 - Subgroup analyses will be performed by the primary endpoint categorized by type of AMI (STEMI vs NSTEMI), Subgroup analyses will be performed by the primary endpoint categorized by Type of AMI (STEMI vs NTEMI), Gender, Age (≥75 vs <75), Diabetes, LVEF (≥40% vs <40%), eGFR (≥60 vs <60), type of implanted stents (Xience vs Resolute vs Synergy stents), Bleeding risk according to the ARC criteria (high vs low bleeding risk), CYP2C19 loss-of-function carrier status (carrier vs non-carrier).
 - The primary analysis population for primary and secondary endpoints will be the Intention-to-Treat (ITT) population. The primary endpoint analysis will also be performed on the Per Protocol (PP) population as subsequent analysis.

 A primary endpoint analysis stratified by the institutions as a sensitivity analysis. Strata will be divided by the accrual number of institution based on quartiles.

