• The hypothesis of non-inferiority test will be based on the difference of proportions. Let r_T denote the true event proportion in the test arm (clopidogrel + aspirin) between 1 and 12 months, and r_C denote the true event proportion in the control arm (ticagrelor + aspirin) between 1 and 12 months. The hypotheses are

$$H_0: r_T - r_C \ge \Delta$$

$$H_A$$
: r_T - r_C < Δ

The∆is the non-inferiority margin, and is taken to be 0.03. The test will be performed as a one-sided test at alpha=0.05.

The null hypothesis shall be rejected at alpha=0.05 if the one-sided p-value is less than 0.05. When this occurs, the upper limit of the two-sided 95% confidence interval will be less than 3%.

- If the non-inferiority analysis passed the acceptance criterion, a superiority analysis will be performed. Statistical superiority is achieved when the upper limit of the two-sided 95% confidence interval of the risk difference is less than 0%. The type I error for this analysis is protected by the non-inferiority analysis, and no alpha adjustment would be appropriate
- Subgroup analyses will be performed by the primary endpoint categorized by type of AMI (STEMI vs NSTEMI), Subgroup analyses will be performed by the primary endpoint categorized by Type of AMI (STEMI vs NTEMI), Gender, Age (≥75 vs <75), Diabetes, LVEF (≥40% vs <40%), eGFR (≥60 vs <60), type of implanted stents (Xience vs Resolute vs Synergy stents), Bleeding risk according to the ARC criteria (high vs low bleeding risk), CYP2C19 loss-of-function carrier status (carrier vs non-carrier).

- The primary analysis population for primary and secondary endpoints will be the Intention-to-Treat (ITT) population. The primary endpoint analysis will also be performed on the Per Protocol (PP) population as subsequent analysis.
- A primary endpoint analysis stratified by the institutions as a sensitivity analysis. Strata will be divided by the accrual number of institution based

on quartiles.

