After applying mathematical formula, the estimated BARC 2, 3 and 5 bleeding would be 4.07% in the ticagrelor group and 2.99% in the clopidogrel group. Thus, the expected event rate of the primary endpoint from 1 to12 months after index PCI was 9.35% (ischemic event of 5.28% + bleeding event of 4.07%) in the ticagrelor group and 9.59% (ischemic event of 6.6% + bleeding event of 2.99%) in the clopidogrel group. We chose the noninferiority margin in accordance with clinical judgment and other relevant studies with a noninferiority design at the present study design. The noninferiority margin of two contemporary trials of antiplatelet treatment after PCI that were available up to that time was equivalent to a 40% increase in the expected event rate^{18, 19}. The steering committee decided that the noninferiority margin in our study should be less than a 40% increase compared to the expected event rate of the control group. After considering clinically acceptable relevance and the feasibility of study recruitment, we finally selected the noninferiority margin of 3.0%, which was equivalent to a 32% increase in the expected event rate. Sample size calculations (PASS 13, NCSS, LLC, Kaysville, Utah, USA) were performed based on one-sided α of 0.05 and a power of 80 %. To achieve these goals, a total of 2,230 patients were needed. After considering a follow-up loss rate of 10%, a total of 2,590 (1,295 patients in each group) patients were required.

357358359

342343

344

345

346

347

348

349350

351

352

353

354

355

356

8. Study Duration

360 IRB approval to Dec. 31st, 2020

361

[figure not shown]
362

[figure not shown]
9. Study Method

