- 315 Concomitant treatment of oral anticoagulant agent (vitamin-K antagonists or novel 316 oral anticoagulants such as dabigatran, rivaroxaban, apixaban, or edoxaban) during 317 the study period 318 Poor compliance Conversion from ticagrelor + aspirin to clopidogrel + aspirin during RCT 319 320 procedure and vice versa 321 Discontinuation of test or control drugs for 7 days or longer 322 * In the cases of withdrawal of consent, concomitant treatment of oral anticoagulation 323 agent and poor compliance, their data will be used for statistical analyses until such 324 events occur. 325 326 8.3 Primary endpoint analysis 327 328 The non-inferiority test between 1 and 12 months after AMI will be based on the 329 Kaplan-Meier estimates. A 95% two-sided confidence interval will be computed for 330 the difference event rate (clopidogrel + aspirin) - event rate (ticagrelor + aspirin). 331 The clopidogrel group will be judged as non-inferior to the ticagrelor if the upper 332 confidence limit is less than the predetermined non-inferiority margin of 3% (absolute 333 risk difference). 334 The hypothesis of non-inferiority test will be based on the difference of proportions. 335 Let r_T denote the true event proportion in the test arm (clopidogrel + aspirin) between 336 1 and 12 months, and r_C denote the true event proportion in the control arm (ticagrelor + aspirin) between 1 and 12 months. The hypotheses are 337 338 $H_0: r_T - r_C \ge \Delta$ H_A : r_T - r_C < Δ 339 340 The∆is the non-inferiority margin, and is taken to be 0.03. The test will be performed 341 as a one-sided test at alpha=0.05. 342 The null hypothesis shall be rejected at alpha=0.05 if the one-sided p-value is less 343 than 0.05. When this occurs, the upper limit of the two-sided 95% confidence interval
 - The stratified log-rank test will be performed to test the comparison between time to event distribution Stratification factors will be prior use of STEMI (yes or no).

345

346

will be less than 3%.

- Unless otherwise specified, the stratified hazard ratio between two treatment groups along with CI will be obtained by fitting a stratified Cox model with the treatment group variables as unique covariate. Stratification factors will be same as above.
- If the non-inferiority analysis passed the acceptance criterion, a superiority analysis

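### The primary non-inferiority rule is written at two error rates, one-sided 0.05 and a two-sided 95% interval, and the plan wrongly says the first guarantees the second

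*Protocol*

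**What the plan says.** Protocol section 14.3.1 describes one primary hypothesis and gives two ways to accept it.

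- **Interval rule.** The interval is defined by "A 95% two-sided confidence interval will be computed for the difference event rate (clopidogrel + aspirin) – event rate (ticagrelor + aspirin"), and clopidogrel is "judged as non-inferior to the ticagrelor if the upper confidence limit is less than the predetermined noninferiority margin of 3% (absolute risk difference").
- **P-value rule.** The margin "is the non-inferiority margin, and is taken to be 0.03", the test is one-sided at 0.05, and "The null hypothesis shall be rejected at alpha=0.05 if the one-sided p-value is less than 0.05".
- **Stated link.** The next sentence joins the two: "When this occurs, the upper limit of the two-sided 95% confidence interval will be less than 3" per cent.

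The Statistical Analysis part of the Protocol Summary repeats all three elements and later restates the 95% interval criterion in a separate paragraph. SAP section 8.3 repeats the p-value rule ("The null hypothesis shall be rejected at alpha=0.05 if the one-sided p-value is less" than 0.05) beside the 95% interval. The sample-size calculations in Protocol 7.3.2 and SAP 8.1 "were performed based on one-sided α of 0.05 and a power of 80" per cent. The follow-on superiority test uses the two-sided 95% interval.

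**The concern.** An upper 95% limit below 3% requires a one-sided p-value below 0.025. A one-sided p-value below 0.05 requires only that the upper **90%** limit be below 3%. The implication therefore runs in one direction: passing the interval rule guarantees passing the p-value rule, and the plan asserts the reverse.

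For one-sided p between 0.025 and 0.05 the same data are non-inferior under one sentence and not under another. The false-positive rate at the margin is 2.5% or 5% depending on the sentence used, and the plan claims both. In an open-label trial, a choice between two written rules should not still be open when the data are seen.

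**Working it through.** **Inputs.** Margin 0.03 (14.3.1). Event rate "9.35% (ischemic event of 5.28% + bleeding event of 4.07%) in the ticagrelor group" and 9.59% for clopidogrel (7.3.2). 1,165 efficacy cases per arm, 1,295 after adding 10% loss (table in 7.3.1). One-sided 0.05 and 80% power (7.3.2). Normal quantiles: 1.645 (one-sided 0.05), 1.960 (one-sided 0.025), 0.842 (80% power). Standard errors use the unpooled normal approximation without censoring.

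**1. The plan's sample size.** With 9.35% in both arms,

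n = (1.645 + 0.842)² × 2 × 0.0935 × 0.9065 / 0.03² = 1,165 per arm; 1,165 / 0.9 = 1,295 after rounding up.

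This matches the table, so the trial was sized on the p-value rule with equal rates. With the stated 9.59% for clopidogrel, the same rule would need 1,392 per arm.

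**2. Where each rule passes.** The p-value rule passes if the observed difference is below 0.03 − 1.645 × SE; the interval rule passes if it is below 0.03 − 1.960 × SE.

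| Per arm | Rates | SE (points) | P-value rule passes below | Interval rule passes below |
|---|---|---|---|---|
| 1,295 | 9.35% both | 1.144 | +1.12 | +0.76 |
| 1,165 | 9.35% both | 1.206 | +1.02 | +0.64 |
| 1,165 | 9.35% / 9.59% | 1.213 | +1.00 | +0.62 |

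At exactly p = 0.05, with 1,295 per arm and equal rates, the upper 95% limit is 1.12 + 1.960 × 1.144 = 3.36%, which is above the margin.

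**3. A counterexample.** Take 1,165 per arm, 109 events on ticagrelor (9.36%) and 118 on clopidogrel (10.13%). The difference is 0.77 points and the SE 1.23 points. The one-sided p-value is 0.035, which passes. The upper 90% limit is 2.79%, but the upper 95% limit is 3.18%, which fails. With 109 ticagrelor events, every clopidogrel count from 117 to 120 gives this split; 116 passes both rules and 121 fails both.

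**4. Probability of disagreement.** Power is Φ[(0.03 − true difference)/SE − z], and the disagreement probability is the gap between the two powers.

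| Per arm | True rates | Power, one-sided 0.05 | Power, one-sided 0.025 | Rules disagree |
|---|---|---|---|---|
| 1,295 | 9.35% / 9.59% | 77.5% | 67.0% | 10.5% |
| 1,165 | 9.35% / 9.59% | 73.6% | 62.4% | 11.2% |
| 1,295 | 9.35% both | 83.6% | 74.6% | 9.0% |
| 1,165 | 9.35% both | 80.0% | 70.1% | 9.9% |

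**5. Sample size for 80% power under the interval rule.** Equal rates: (1.960 + 0.842)² × 2 × 0.0935 × 0.9065 / 0.03² = 1,479 per arm, or 1,644 after 10% loss. Stated rates: 1,767 per arm, or 1,964 after loss.

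**The case against.** The rules agree about 90% of the time under the planning rates, and a result that passes the 95% interval passes both. The superiority claim cannot be affected, because an upper 95% limit below zero satisfies either non-inferiority rule. This limits the damage to the non-inferiority claim, but that claim is the trial's primary conclusion.

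A second objection is that one-sided 0.025 is not the only coherent repair. Keeping one-sided 0.05 and judging non-inferiority on the two-sided 90% interval would also work. It agrees with the sample-size sections and is the only choice under which the planned number keeps 80% power at equal rates. That is true, and the documents do not force either choice. But it would mean rewriting the acceptance criterion everywhere the 95% interval appears, and the linking sentence would still have to be corrected.

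A third is that the figures are normal approximations, while the plan uses Kaplan-Meier estimates. Kaplan-Meier standard errors would move the limits slightly. They cannot reconcile 0.025 with 0.05.

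**Conclusion.** The concern holds. The linking sentence is mathematically wrong, the two rules differ by a factor of two in type I error, and no section says which prevails. On the plan's own event rates, about one trial in ten would produce data on which the rules conflict: 10.5% at 1,295 per arm and 11.2% at 1,165, assuming complete follow-up at those numbers. The size of that band depends on the event rates and on the approximation; the contradiction does not. Because it sits in the primary decision rule, it must be fixed before analysis.

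**What to change.** State one rule: non-inferiority is declared if the upper limit of the two-sided 95% confidence interval for clopidogrel minus ticagrelor is below 3.0 percentage points, equivalent to a one-sided p-value below 0.025. This keeps the acceptance criterion already written and matches the interval used for superiority.

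- Replace the one-sided 0.05 by 0.025 in the Protocol Summary, Protocol 14.3.1 and SAP 8.3. The linking sentence then becomes true.
- Carry 0.025 into Protocol 7.3.2 and SAP 8.1 and restate the power there, naming the rates and the number per arm used.
- Check that the Summary's separate restatement of the 95% interval criterion agrees.

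The text change is a few sentences and needs no extra patients if the lower power is accepted. Like for like at equal rates, power goes from 80.0% to 70.1% at 1,165 per arm and from 83.6% to 74.6% at 1,295. At the stated rates it is 62.4% and 67.0% respectively. Restoring 80% power would mean randomising 1,644 per arm (equal rates) or 1,964 per arm (stated rates), against 1,295 planned. If the sponsor prefers one-sided 0.05, every 95% interval in the non-inferiority criterion must become a 90% interval, and the 5% error rate should be stated openly.
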